7.4. Study Visits (Days 1-4)

Refer to Tables 1 and 3 for schedule of procedures at study visits following Baseline. Procedures to be performed by the following personnel: PI, Study Coordinator, Research Nurse, and/or EEG technician.

Hour 4 Visit

- **Second EEG recording:** With the cap in place from the baseline recording, electrode impedance will be measured, and electrode gel refilled to ensure proper fit. A second EEG will be recorded during an 8-minute resting state with eyes opened and closed at regular intervals. The cap will remain on the subject until the end of the Hour 8 recording but will not be recording continuously between sessions.
- **Self-Report measures:** Electronic versions of the following surveys will be administered: SMDDS, EPDS, STAI (Y1), and SCS.

- **Semi-Structure interview & iMotions Recording:** Facing a laptop equipped with a standard camera and microphone and iMotions Affectiva software, the subject will be administered a semi-structured interview about depressive symptoms and affect by study personnel. Interview questions will include a modified version of the HAM-D (items suitable for repeated measure within the same day) and additional questions to assess the subject's experiences of enjoyment, guilt, and irritability. The interview and recording will last 10-20 minutes. The memory probe task will be completed, in which a subject will be told the predetermined word or phrase to cue recall of the sad and happy events, while the camera records her facial expressions for 30 seconds for each event and the subject rates her emotional experience.

Hour 8 Visit

- **Third EEG recording:** With the cap in place from the Hour 4 recording, electrode impedance will be measured, and electrode gel refilled to ensure proper fit. A third EEG will be recorded during an 8-minute resting state with eyes opened and closed at regular intervals. Following completion of this recording, the cap will be removed.
- **Self-Report measures:** Electronic versions of the following surveys will be administered: SMDDDS, EPDS, STAI (Y1), and SCS.
- **Semi-Structured interview and iMotions Recording:** Facing a laptop equipped with a standard camera and microphone and iMotions Affectiva software, the subject will be administered a semi-structured interview about depressive symptoms and affect by study personnel. Interview questions will include a modified version of the HAM-D (items suitable for repeated measure within the same day) and additional questions to assess the subject's experiences of enjoyment, guilt, and irritability. The interview and recording will last 10-20 minutes. The memory probe task will be completed, in which a subject will be told the predetermined word or phrase to cue recall of the sad and happy events, while the camera records her facial expressions for 30 seconds for each event and the subject rates her emotional experience.

Hour 28 Visit (4 hours after highest dose of brexanolone begins)

- **Blood sample:** to measure and document peak circulating levels of allopregnanolone
- **Fourth EEG recording:** EEG cap will be fitted by technician and electrodes filled with gel solution. Impedance will be measured to ensure proper adherence to scalp. Cap set-up will take approximately 20 minutes. A fourth EEG will be recorded during an 8-minute resting state with eyes opened and closed at regular intervals. The cap will be removed following this recording.
- **Self-Report measures:** Electronic versions of the following surveys will be administered: SMDDDS, EPDS, STAI (Y1), and SCS.
- **Semi-Structured interview and iMotions Recording:** Facing a laptop equipped with a standard camera and microphone and iMotions Affectiva software, the subject will be administered a semi-structured interview about depressive symptoms and affect by study personnel. Interview questions will include the HAM-D and additional questions to assess the subject's experiences of

enjoyment, guilt, and irritability. The interview and recording will last 10-20 minutes. The memory probe task will be completed, in which a subject will be told the predetermined word or phrase to cue recall of the sad and happy events, while the camera records her facial expressions for 30 seconds for each event and the subject rates her emotional experience.

Hour 60

- **Brexanolone infusion concludes**

SAFETY MONITORING DURING INTERVENTION PHASE (Every 2 hours, while awake, during infusion)

Continuous Pulse Oximetry

Subjects will be monitored for hypoxia throughout intervention phase using continuous pulse oximetry equipped with an alarm. Oxygen saturation need only be recorded in the event of hypoxia, in which case, the event is to be recorded as an AE. The infusion will be immediately stopped if pulse oximetry reveals hypoxia. After an episode of hypoxia, the infusion should not be resumed.

Monitoring for Excessive Sedation and Loss of Consciousness

For the duration of the infusion, subjects must be assessed for excessive sedation and loss of consciousness by a healthcare provider every 2 hours during planned, non-sleep periods. If excessive sedation or loss of consciousness occurs at any time during the infusion, the infusion will be stopped until the symptoms resolve. The infusion may be resumed at the same or lower dose as clinically appropriate (see Section 6.1), and an AE is to be recorded.

Vital Signs

Vital signs include oral temperature (°C), respiratory rate, heart rate, and blood pressure. Heart rate and blood pressure to be collected in supine position at all scheduled time points as well as in the standing position at specific time points listed in Table 3.

7.5. Phone Contact

Subjects will be provided phone and email contact information for PI and Study Coordinator, should the participant have questions or concerns that may be addressed over the phone between in-person visits.

7.6. Final Visit (Hour 72)

Refer to Tables 1 and 3 for schedule of procedures at final inpatient visit. Procedures to be performed by the following personnel: PI, Study Coordinator, Research Nurse, and/or EEG technician.

Hour 72 Visit (12 hours after the end of brexanolone infusion)

- **Fifth EEG recording:** EEG cap will be fitted by technician and electrodes filled with gel solution. Impedance will be measured to ensure proper adherence to scalp. Cap set-up will take approximately 20 minutes. A fifth and final EEG will be recorded during an 8-minute resting state

with eyes opened and closed at regular intervals. The cap will be removed following this recording.

- **Self-Report measures:** Electronic versions of the following surveys will be administered: C-SSRS, EPDS; STAI (Y1&Y2); SCS; BIMF; IDS-SR; RRS-10; SHAPS.
- **Semi-Structured interview and iMotions Recording:** Facing a laptop equipped with a standard camera and microphone and iMotions Affectiva software, the subject will be administered a semi-structured interview about depressive symptoms and affect by study personnel. Interview questions will include the HAM-D and additional questions to assess the subject's experiences of enjoyment, guilt, and irritability. The interview and recording will last 10-20 minutes. The memory probe task will be completed, in which a subject will be told the predetermined word or phrase to cue recall of the sad and happy events, while the camera records her facial expressions for 30 seconds for each event and the subject rates her emotional experience.
- **Blood sample:** to measure and document a return to baseline circulating levels of allopregnanolone
- **Safety Check prior to discharge from UNC Women's Hospital**
 - Vital signs
 - C-SSRS ("since last visit")
 - Review of concomitant medications and nonpharmacological interventions administered during hospital stay

In the unlikely event that there is imminent risk of suicidal behavior at the time of the final safety check, the subject will be withdrawn from the research study, discharged from the Women's Hospital, and referred to the UNC Emergency Department and/or other appropriate inpatient hospitalization. The study doctor will provide referrals for continued care, which may include hospitalization, but will not be responsible for providing such care following withdrawal from the research study.

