6.5. Rescue Medications and Procedures (if applicable)

Since subjects will be hospitalized inpatients, and since they will be treated with a GABA positive allosteric modulator, which has known anxiolytic effects, it is not anticipated that anyone would experience a worsening of symptoms; if there was a concern that rescue was required, the response would take the form of decreasing or discontinuing the brexanolone and treating the subject with conservative measures until the response to drug discontinuation could be assessed.

6.6.Compliance Checks

Study drug will be prepared by a pharmacist or designee, administered as a continuous IV infusion, and the dose received will be documented in the study record. There should be no adjustments in dosing except as described in Section 6.1.

6.7.Withdrawal / Discontinuation of Enrolled Participants

Enrolled participants may be withdrawn if new or worsening symptoms or any adverse event suggest that continued participation would place the subject at risk and not be in the subject's best interest.

Subjects may withdraw from the study at any time for any reason without compromising the subject's medical care. The Investigator will also withdraw subjects upon the request of Sage Therapeutics or upon termination of the study.

Subjects who withdraw should, if possible, complete an early termination visit, which includes the assessments for the Hour 72 visit (see Table 3).

The reasons for protocol discontinuation and/or subject withdrawal from the study will be recorded in the study record.

6.8.Voluntary Withdrawal (Drop-Out) of Enrolled Participants

The subjects may voluntarily withdraw participation at any time, for any reason, with no penalty or loss of rights. Reasons for discontinuation will be documented in the database.

7. Study Procedures and Schedule

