7.7. Follow-Up Contact (Day 30 ± 3)

Refer to Tables 1 and 3 for schedule of procedures at final inpatient visit. Procedures to be performed by PI and Study Coordinator.

Day 30 Visit

This follow-up visit will occur in-person, on the phone, or over HIPAA-secured Zoom call, depending on the subject's preference.

- **Self-Report Measures:** Electronic versions of the following surveys will be administered: EPDS; STAI (Y1&Y2); SCS; BIMF; IDS-SR; RRS-10; SHAPS.
- **Semi-Structured interview:** Study coordinator or PI will administer the HAM-D
- **Exit Interview:** an informal interview with PI to include items such as:
 - What is your mood like today?
 - Do you feel the same as, worse than, or better than you did when you left the hospital? (If worse than, when did your mood start to decline?)
 - Have you had any trouble with your thinking?

- How stressed do you feel? Have you had any stressful life events since leaving the hospital?
- Do you have any current illnesses?
- How would you describe your experience participating in this research study?
- Do you have any feedback you'd like to share about your experience in this study or with the study drug?

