7.8. Premature Discontinuation

If a subject withdraws or the investigator discontinues subject participation, the subject will be offered the optional exit interview session with PI to discuss her experience in the study protocol and assessment conducted while enrolled. Safety assessments will be performed on subjects who withdraw prematurely following initiation of brexanolone and include the following: clinical lab assessments, vital signs, 12-lead ECG, C-SSRS, and evaluation of adverse events.

In the unlikely event that there is imminent risk of suicidal behavior at the time of the final safety check, the subject will be withdrawn from the research study, discharged from the Women's Hospital, and referred to the UNC Emergency Department and/or other appropriate inpatient hospitalization. The study doctor will provide referrals for continued care, which may include hospitalization, but will not be responsible for providing such care following withdrawal from the research study.

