- Pay close attention to any changes, especially sudden changes in mood, behavior, thoughts, or feelings, or if they develop suicidal thoughts or actions.
- Tell the healthcare provider or study doctor right away if they have any new or sudden changes in mood, behavior, thoughts, or feelings during the study.
- Keep all follow-up visits with the subject's regular doctor.
- Contact the study or regular doctor if they have concerns about these symptoms after the infusion has been completed.

Subjects will be instructed to tell the study or regular doctor right away if they have any of the following symptoms, especially if they are new, worse, or worrying the subject:

- attempts to commit suicide and/or harm themselves
- new or worse depression
- other unusual changes in behavior or mood

If the subject has thoughts of harming themselves or others, they will be instructed to go to the nearest emergency department (ED) or call 911. They can also call the National Suicide Prevention Lifeline 24 hours a day at [name].

If there is imminent risk of suicidal behavior at the time of the final safety check (Hour 72 prior to discharge), the subject will be withdrawn from the research study, discharged from the Women's Hospital, and referred to the UNC Emergency Department and/or other appropriate inpatient hospitalization. The study doctor will provide referrals for continued care, which may include hospitalization, but will not be responsible for providing such care following withdrawal from the research study.

Risks Associated with BRX: The following adverse events in the PPD clinical program are considered the most common (more than 1 in 20 people and at least twice the rate of placebo) side effects of brexanolone:

- Sedation (drowsiness) / somnolence (sleepiness)
- Dry mouth
- Passing out (loss of consciousness)
- Flushing of the skin or face (flushing/hot flush)

Other side effects that have occurred in ≥ 2% and > placebo include:

- Faster than normal heart rate (tachycardia)
- Diarrhea
- Upset stomach (dyspepsia)
- Dizziness, feeling faint (presyncope), feeling of losing one's balance (vertigo)
- Mouth and throat pain (oropharyngeal pain)

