The study coordinator or research nurse will monitor side effects and AEs every two hours when the patient is awake and receiving the infusion. Adverse events forms will also be completed after each EEG session and will include the assessment of EEG-related AEs, including discomfort and irritation from the EEG net and electrode gel. Side effects consistent with moderate or severe AEs or that are troublesome to the subject will also be immediately reported to the inpatient unit nurses and to [name], who will be responsible for determining the next course of action, which might include slowing or discontinuing the infusion or discontinuation of the subject from the study. [name] will review all protocol data monthly, including enrollment and retention statistics and aggregate reports of side effects/AEs. As the contact PI, [name] will be the one responsible to report all AEs reported as severe to the IRB within one week. The study sponsor will be notified of any study modifications or suspension imposed by the local IRB in response to an AE. Finally, it should be noted that the subjects will be hospitalized on an inpatient unit during the entire administration of BRX and will not be discharged until clinically cleared by the physician.

Reporting and Documentation Procedures:

All SAEs (regardless of causality) will be recorded from the signing of the consent form(s) until the final visit of the study for that subject. Serious adverse events occurring after the subject's final study visit should be reported to the Sponsor or Sponsor's designee only if the investigator considers the SAE to be related to study drug.

All SAEs must be reported to Sage Therapeutics, or designee, immediately. A written account of the SAE must be sent to Sage Therapeutics within 24 hours of the first awareness of the event by the Investigator and/or his/her staff to the IQVIA email address: [contact]. The Investigator must complete, sign and date the SAE report form, verify the accuracy of the information recorded on the SAE report form with the corresponding source documents, and send a copy to Sage Therapeutics, or designee.

Additional follow-up information, if required or available, must be sent to Sage Therapeutics, or designee, within 24 hours of receipt; a follow-up SAE form should be completed and placed with the original SAE information and kept with the appropriate section of the study file.

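### Withdrawing a woman at imminent suicide risk at the Hour 72 check removes only one scheduled study contact, her Day 30 follow-up

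*Combined protocol and SAP*

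**What the plan says.** Section 7.6 sets the rule for the pre-discharge check: "In the unlikely event that there is imminent risk of suicidal behavior at the time of the final safety check, the subject will be withdrawn". Her participation in the study then ends: she leaves the Women's Hospital with a referral to the Emergency Department or other inpatient care. The study doctor gives referrals but takes no responsibility for later care. Section 7.8 repeats the rule. Section 10.1 repeats it and names the time: "imminent risk of suicidal behavior at the time of the final safety check (Hour 72 prior to discharge), the subject will be withdrawn".

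The protocol provides four things for women who leave early:

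- Section 6.7: "Subjects who withdraw should, if possible, complete an early termination visit, which includes the assessments for the Hour 72 visit".
- Section 7.8: "Safety assessments will be performed on subjects who withdraw prematurely following initiation of brexanolone". These are laboratory tests, vital signs, ECG, C-SSRS and adverse-event evaluation, with no later date set.
- Section 7.8 also: "the subject will be offered the optional exit interview session with PI".
- Section 7.5: telephone and email details, to be used if she has questions.

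Follow-up is a single contact at Day 30 (±3). Section 7.7 says: "This follow-up visit will occur in-person, on the phone, or over HIPAA-secured Zoom call", as the woman prefers.

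On safety recording, section 10.3 says: "All SAEs (regardless of causality) will be recorded from the signing of the consent form(s) until the final visit of the study for that subject". After that visit an SAE is reported "only if the investigator considers the SAE to be related to study drug".

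**The concern.** Withdrawal usually protects a participant from further exposure or burden. Here there is little left to protect her from. Dosing stopped 12 hours earlier and the fifth EEG is part of the same visit. Withdrawal may spare her any Hour 72 research tasks not yet done, but after that visit it removes only the follow-up contact.

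Section 10.1 lists suicidal thoughts or actions as a serious risk of the drug in some people aged 24 and younger, and the study enrols from age 18. The woman just found to be at highest risk is therefore the one whom the study stops contacting on its own initiative. Related events remain reportable, but the site can report only what it learns of. Without a scheduled contact, that depends on her or her clinicians coming forward. The same gap applies to any dosed woman who stops early under 6.7 or 7.8, since neither section keeps Day 30 for her.

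**Working it through.** **Check that nothing is scheduled after Day 30.** The synopsis gives 7 weeks of participation. Inputs: screening of up to 14 days (7.2), infusion of 60 h = 2.5 days (4.1), follow-up 30 days after the infusion ends (section 4), window of 3 days (7.7).

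- Counting from the end of infusion: 14 + 2.5 + 30 + 3 = 49.5 days; 49.5 / 7 = 7.1 weeks.
- Counting Day 30 + 3 from Day 1: about 14 + 33 = 47 days; 47 / 7 = 6.7 weeks.

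Both round to the stated 7 weeks, so Day 30 is the last planned contact.

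**Contacts removed.** Table 3 has one column after Hour 72, the Day 30 follow-up. The early-termination visit in 6.7 repeats the Hour 72 assessments that she has already reached. The 7.8 safety assessments are tied to the withdrawal itself. The 7.5 phone contact is initiated by her. Scheduled contacts after Hour 72 = 1; removed by withdrawal = 1. That she loses Day 30 is an inference from being withdrawn from the study: no sentence says that withdrawn women skip it, and none says that they keep it.

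**Scales removed.** Section 7.7 lists HAM-D, EPDS, STAI, SCS, BIMF, IDS-SR, RRS-10 and SHAPS = 8. Tables 1 and 3 also place the SMDDS at Day 30, giving 9. Table 1 does not schedule the IDS-SR at Day 30; its use then rests on Table 3 and 7.7.

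**SAE recording.** The subject's final visit in 10.3 is not defined. Section 5.3 puts exit interviews at the final study visit and 7.7 puts them at Day 30, which favours Day 30. The heading of 7.6 calls Hour 72 the final visit. Hour 72 is 72 / 24 = 3.0 days from the start of infusion.

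| Reading of final visit | All-cause recording lost, relative to other women | With ±3 days |
|---|---|---|
| Day 30, counted from Day 1 | 29.0 − 3.0 = 26.0 days | 23.0 to 29.0 |
| 30 days after infusion end | 60 + 720 = 780 h; (780 − 72) / 24 = 29.5 days | 26.5 to 32.5 |
| Hour 72 | 0 days | 0 |

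On the first two readings the loss is mainly of later SAEs judged unrelated. A hospitalization that follows the Hour 72 finding would probably be recorded, because inpatient admission meets the SAE definition in 10.3. That section also treats a possible relationship as related, and sets no time limit on reporting related SAEs.

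**The case against.** The strongest reply is that Day 30 is not a suicide-safety visit. Table 3 appears to schedule no C-SSRS then and 7.7 lists none, so no scheduled C-SSRS is lost, and a call about four weeks later does little for someone in immediate danger. Her protection is the referral to emergency or inpatient care, the emergency instructions in 10.1, her regular doctor, and the telephone and email access in 7.5. All of this stands. It limits the point to follow-up and safety capture.

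It can also be said that withdrawal spares her something. The Hour 72 visit includes recall of a sad memory, and 7.6 does not fix the order of tasks. If the C-SSRS comes first, stopping could spare her that task. This is a reason to stop research procedures at once, but not a reason to cancel Day 30.

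A reader might draw three stronger conclusions that the documents do not support:

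- *She is left without care or loses her exit interview.* Referral is specified, and 7.8 still offers the interview, though it is optional and undated.
- *Her SAE recording is certainly cut short.* That depends on an undefined term, and on one reading the relative loss is zero.
- *The rule distorts primary outcome 2.* A woman who does not complete follow-up is correctly counted as a non-completer, and the outcome is a descriptive count with no test.

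**Conclusion.** The point holds and is minor. Three sections state the rule outright, and at Hour 72 its one effect on the remaining schedule is to remove the Day 30 contact. The cost per affected woman is 1 study-initiated contact with 8 or 9 scales. There is also between 0 and 32.5 days of all-cause SAE recording, depending on how 10.3 is read and on the visit window.

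This rests on two assumptions: that withdrawal from the research study cancels Day 30, which no section contradicts, and that no follow-up arrangement exists outside the document. The protocol describes the event as unlikely and gives no frequency, so no expected number of cases is claimed. Acute care is provided for, and related or possibly related SAEs stay reportable. What remains is a small gap that is cheap to close.

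**What to change.** - **Sections 7.6, 7.8 and 10.1:** replace withdrawal from the research study with: *stop any remaining research procedures, refer for acute care, and keep the Day 30 (±3) phone or video safety contact unless consent is withdrawn.*
- **Sections 6.7 and 7.8:** keep the same Day 30 contact for any woman who received brexanolone and stops early.
- **Section 10.3:** replace the undefined end of all-cause SAE recording with Day 30 (±3) for every dosed woman. State whether Day 30 counts from Day 1 or from the end of infusion.
- **Section 7.7:** list an adverse-event review. The adverse-event row of Table 3 is broken in the text available here, so it cannot show whether the review is already marked at follow-up.

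A C-SSRS at Day 30 for all women is an optional addition that this repair does not need.

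The cost is one amendment, matching consent wording and a few extra remote contacts, some of which will not be reached.
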